### 9.1 Methods of Measurement

- CT and MRI are the best currently available and reproducible methods to measure target lesions selected for response assessment. Conventional CT and MRI should be performed with cuts of 10 mm or less in slice thickness contiguously. Spiral CT should be performed using a 5 mm contiguous reconstruction algorithm. This applies to tumors of the chest, abdomen and pelvis. Head and neck tumors and those of extremities usually require specific protocols.
- Lesions on chest X-ray are acceptable as measurable lesions when they are clearly defined and surrounded by aerated lung. However, CT is preferable.
- When the primary endpoint of the study is objective response evaluation, ultrasound (US) should not be used to measure tumor lesions. It is, however, a possible alternative to clinical

measurements of superficial palpable lymph nodes, subcutaneous lesions and thyroid nodules. US might also be useful to confirm the complete disappearance of superficial lesions usually assessed by clinical examination.

- The utilization of endoscopy and laparoscopy for objective tumor evaluation has not yet been fully and widely validated. Their uses in this specific context require sophisticated equipment and a high level of expertise that may only be available in some centers. Therefore, the utilization of such techniques for objective tumor response should be restricted to validation purposes in specialized centers. However, such techniques can be useful in confirming complete pathological response when biopsies are obtained.
- Tumor markers alone cannot be used to assess response. If markers are initially above the upper normal limit, they must normalize for a patient to be considered in complete clinical response when all lesions have disappeared.
- Cytology and histology can be used to differentiate between PR and CR in rare cases (e.g., after treatment to differentiate between residual benign lesions and residual malignant lesions in tumor types such as germ cell tumors).

### **Baseline documentation of “Target” and “Non-Target” lesions**

- All measurable lesions up to a maximum of five lesions per organ and 10 lesions in total, representative of all involved organs should be identified as *target lesions* and recorded and measured at baseline.
- Target lesions should be selected on the basis of their size (lesions with the longest diameter) and their suitability for accurate repeated measurements (either by imaging techniques or clinically).
- A sum of the longest diameter (LD) for *all target lesions* will be calculated and reported as the baseline sum LD. The baseline sum LD will be used as reference by which to characterize the objective tumor.
- All other lesions (or sites of disease) should be identified as *non-target lesions* and should also be recorded at baseline. Measurements of these lesions are not required, but the presence or absence of each should be noted throughout follow-up.

## **9.2 Response Criteria**

### **9.2.1 Evaluation of target lesions**

- \* Complete Response (CR): Disappearance of all target lesions
- \* Partial Response (PR): At least a 30% decrease in the sum of the LD of target lesions, taking as reference the baseline sum LD

- \* Progressive Disease (PD): At least a 20% increase in the sum of the LD of target lesions, taking as reference the smallest sum LD recorded since the treatment started or the appearance of one or more new lesions
- \* Stable Disease (SD): Neither sufficient shrinkage to qualify for PR nor sufficient increase to qualify for PD, taking as reference the smallest sum LD since the treatment started

### 9.2.2 Evaluation of non-target lesions

- \* Complete Response (CR): Disappearance of all non-target lesions and normalization of tumor marker level
- \* Incomplete Response/ Stable Disease (SD): Persistence of one or more non-target lesion(s) or/and maintenance of tumor marker level above the normal limits
- \* Progressive Disease (PD): Appearance of one or more new lesions and/or unequivocal progression of existing non-target lesions (1)

(1) Although a clear progression of “non-target” lesions only is exceptional, in such circumstances, the opinion of the treating physician should prevail and the progression status should be confirmed later on by the review panel (or study chair).

### 9.2.3 Evaluation of best overall response

The best overall response is the best response recorded from the start of the treatment until disease progression/recurrence (taking as reference for PD the smallest measurements recorded since the treatment started). In general, the patient's best response assignment will depend on the achievement of both measurement and confirmation criteria.

Target lesions	Non-Target lesions	New Lesions	Overall response
CR	CR	No	CR
CR	Incomplete response/SD	No	PR
PR	Non-PD	No	PR
SD	Non-PD	No	SD

PD	Any	Yes or No	PD
Any	PD	Yes or No	PD
Any	Any	Yes	PD

- Patients with a global deterioration of health status requiring discontinuation of treatment without objective evidence of disease progression at that time should be classified as having “symptomatic deterioration”. Every effort should be made to document the objective progression even after discontinuation of treatment.
- In some circumstances it may be difficult to distinguish residual disease from normal tissue. When the evaluation of complete response depends on this determination, it is recommended that the residual lesion be investigated (fine needle aspirate/biopsy) to confirm the complete response status.

#### 9.2.4 Confirmation

- The main goal of confirmation of objective response is to avoid overestimating the response rate observed. In cases where confirmation of response is not feasible, it should be made clear when reporting the outcome of such studies that the responses are not confirmed.
- To be assigned a status of PR or CR, changes in tumor measurements must be confirmed by repeat assessments that should be performed no less than 4 weeks after the criteria for response are first met. Longer intervals as determined by the study protocol may also be appropriate.
- In the case of SD, follow-up measurements must have met the SD criteria at least once after study entry at a minimum interval (in general, not less than 6-8 weeks) that is defined in the study protocol

#### 9.2.5 Duration of overall response

- The duration of overall response is measured from the time measurement criteria are met for CR or PR (whichever status is recorded first) until the first date that recurrence or PD is objectively documented, taking as reference for PD the smallest measurements recorded since the treatment started.

#### 9.2.6 Duration of stable disease

- SD is measured from the start of the treatment until the criteria for disease progression are met, taking as reference the smallest measurements recorded since the treatment started.
- The clinical relevance of the duration of SD varies for different tumor types and grades.

Therefore, it is highly recommended that the protocol specify the minimal time interval required between two measurements for determination of SD. This time interval should take into account the expected clinical benefit that such a status may bring to the population under study.

### **9.2.7 Reporting of results**

- All patients included in the study must be assessed for response to treatment, even if there are major protocol treatment deviations or if they are ineligible. Each patient will be assigned one of the following categories: 1) complete response, 2) partial response, 3) stable disease, 4) progressive disease, 5) early death from malignant disease, 6) early death from toxicity, 7) early death because of other cause, or 8) unknown (not assessable, insufficient data).
- All of the patients who met the eligibility criteria should be included in the main analysis of the response rate. Patients in response categories 4-8 should be considered as failing to respond to treatment (disease progression). Thus, an incorrect treatment schedule or drug administration does not result in exclusion from the analysis of the response rate. Precise definitions for categories 4-8 will be protocol specific.
- All conclusions should be based on all eligible patients.
- Sub-analyses may then be performed on the basis of a subset of patients, excluding those for whom major protocol deviations have been identified (e.g., early death due to other reasons, early discontinuation of treatment, major protocol violations, etc.). However, these sub-analyses may not serve as the basis for drawing conclusions concerning treatment efficacy, and the reasons for excluding patients from the analysis should be clearly reported.
- The 95% confidence intervals should be provided

## **10 REGULATORY AND REPORTING REQUIREMENTS**

### **10.1 Protocol Amendments**

Any changes to the protocol will be made in the form of an amendment and must be approved by CTEP and the IRB before implementation.

### **10.2 Informed Consent**

An investigator will explain to each subject (or legally authorized representative) the nature of the study, its purpose, procedures involved, expected duration, potential risks and benefits. Each subject will be informed that participation in the study is voluntary and that he may withdraw from the study at any time, and that withdrawal of consent will not affect her subsequent medical treatment. This informed consent will be given by means of a standard written statement and will be submitted for IRB approval prior to use. No patient will enter the study before her informed

consent has been obtained.

### 10.3 Adverse Events

Expedited adverse event (AE) reporting for this study is via CTEP-AERS (CTEP Adverse Event Reporting System), accessed via the secure CTEP website: (<https://eapps-ctep.nci.nih.gov/ctepaers/pages/task?rand>). The reporting procedures are presented in the “CTEP, NCI Guidelines: Adverse Event Reporting Requirements” and can be downloaded from: (<http://ctep.cancer.gov/protocolDevelopment/electronicapplications/docs/aeguidelines.pdf>).

The descriptions and grading scales found in the CTEP Active Version of the NCI Common Terminology Criteria for Adverse Events (CTCAE) will be utilized for adverse event reporting. The CTEP Active Version of the CTCAE is identified and located on the CTEP website at: [http://ctep.cancer.gov/protocolDevelopment/electronic\\_applications/ctc.htm](http://ctep.cancer.gov/protocolDevelopment/electronic_applications/ctc.htm). All appropriate treatment areas should have access to a copy of the CTEP Active Version of CTCAE. A list of adverse events that have occurred or might occur (Comprehensive Adverse Events and Potential Risks list) can be found in Section 6 (Pharmaceutical Information). A copy of the current Agent-Specific Adverse Event List (ASAEL) is sent with LOI approval letters. The ASAEL is updated periodically; copies of the updated list are available on request via e-mail from [[contact]](mailto:[contact]).

Information about all adverse events, whether volunteered by the subject, discovered by investigator questioning, or detected through physical examination, laboratory test or other means, will be collected, recorded, and followed as appropriate.

All adverse events experienced by subjects will be collected from the time of consent, throughout the study, and until the final study visit. Subjects may be contacted for additional assessments, as necessary.

#### Definitions

Adverse Event (AE): Any undesirable sign, symptom or medical condition occurring after starting study drug (or therapy) even if the event is not considered to be related to the study.

Medical conditions/diseases present before starting study treatment are only considered adverse events if they worsen after starting study treatment (any procedures specified in the protocol). Adverse events occurring before starting study treatment but after signing the informed consent form will be recorded. Abnormal laboratory values or test results constitute adverse events only if they induce clinical signs or symptoms, require therapy or as required by SPEER.

Serious adverse event or reaction: Any untoward medical occurrence that at any dose: results in death, is life-threatening, requires inpatient hospitalization or prolongation of existing hospitalization, results in persistent or significant disability / incapacity, or is a congenital anomaly / birth defect.

The definition of serious adverse event (experience) also includes *important medical event*.

**NCI Protocol #: 7870**

Medical and scientific judgment should be exercised in deciding whether expedited reporting is appropriate in other situations, such as important medical events that may not be immediately life-threatening or result in death or hospitalization but may jeopardize the patient or may require intervention to prevent one of the other outcomes listed in the definition above. These should also usually be considered serious. Examples of such events are intensive treatment in an emergency room or at home for allergic bronchospasm; blood dyscrasias or convulsions that do not result in hospitalization; or development of drug dependency or drug abuse.

Unexpected adverse event: An adverse event, which varies in nature, intensity or frequency from information on the investigational drug/agent provided in the Investigator's Brochure, package insert or safety reports. Any adverse event that is not included in the informed consent is considered "unexpected".

Expected (known) adverse event: An adverse event, which has been reported in the Investigator's Brochure. An adverse event is considered "expected", only if it is included in the informed consent document as a risk.

## **Relationship**

The relationship of all adverse events and serious adverse events to study medication will be assigned as follows:

Definitely: An adverse event which has a timely relationship to the administration of the investigational drug/agent, follows a known pattern of response, for which no alternative cause is present

Probably: An adverse event, which has a timely relationship to the administration of the investigational drug/agent, follows a known pattern of response, but for which a potential alternative cause may be present

Possibly: An adverse event, which has a timely relationship to the administration of the investigational drug/agent, follows no known pattern of response, but a potential alternative cause does not exist.

Unrelated: An adverse event, for which there is evidence that it is definitely related to a cause other than the investigational drug/agent. In general, there is no timely relationship to the administration of the investigational drug/agent, or if there is a timely relationship, the event does not follow a known pattern of response, and there is an alternative cause.

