Unrelated Unlikely	Not Required	Not Required	Not Required	10 Calendar Days	Not Required	10 Calendar Days	Not Required	10 Calendar Days	10 Calendar Days
Possible Probable Definite	Not Required	10 Calendar Days	Not Required	10 Calendar Days	10 Calendar Days	10 Calendar Days	Not Required	24-Hour; 5 Calendar Days	10 Calendar Days

 Adverse events with attribution of possible, probable, or definite that occur greater than 30 days after the last dose of treatment with an agent under a CTEP IND require reporting as follows:

CTEP-AERS 24-hour notification followed by complete report within 5 calendar days for:

- Grade 4 and Grade 5 unexpected events

CTEP-AERS 10 calendar day report:

- Grade 3 unexpected events with hospitalization or prolongation of hospitalization
- Grade 5 expected events

 Although a CTEP-AERS 24-hour notification is not required for death clearly related to progressive disease, a full report is required as outlined in the table.

December 15, 2004

**Note: All deaths on study must be reported using expedited reporting regardless of causality. Attribution to treatment or other cause should be provided.**

- Expedited AE reporting timelines defined:
  - “24 hours; 5 calendar days” – The investigator must initially report the AE via CTEP-AERS within 24 hours of learning of the event followed by a complete CTEP-AERS report within 5 calendar days of the initial 24-hour report.
  - “10 calendar days” - A complete CTEP-AERS report on the AE must be submitted within 10 calendar days of the investigator learning of the event.
- Any medical event equivalent to CTCAE grade 3, 4, or 5 that precipitates hospitalization (or prolongation of existing hospitalization) must be reported regardless of

attribution and designation as expected or unexpected with the exception of any events identified as protocol-specific expedited adverse event reporting exclusions.

- Any event that results in persistent or significant disabilities/incapacities, congenital anomalies, or birth defects must be reported via CTEP-AERS if the event occurs following treatment with an agent under a CTEP IND.
- Use the NCI protocol number and the protocol-specific patient ID provided during trial registration on all reports.

Expedited Adverse Event Reporting Exclusions – Not Applicable

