**NCI Protocol #: 7870**

CRSCompliance for all unanticipated problems and adverse events that are serious and deemed related or possibly related to the research drug, biologic or intervention.

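### *Possibly* related is defined to exclude any potential alternative cause, which steers new event types towards *Unrelated* and removes or slows some expedited reports of unexpected events

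*Combined protocol and SAP*

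**What the plan says.** Section 10.3, under Relationship, gives four attribution categories. The first three all require a timely relationship to dosing and differ as follows:

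- *Definitely*: "follows a known pattern of response, for which no alternative cause is present".
- *Probably*: "follows a known pattern of response, but for which a potential alternative cause may be present".
- *Possibly*: "follows no known pattern of response, but a potential alternative cause does not exist".
- *Unrelated*: an event "for which there is evidence that it is definitely related to a cause other than the investigational drug/agent". A second sentence adds, as a general description, that such events lack a timely relationship or, where timing does fit, show no known pattern and do have an alternative cause.

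The expedited-reporting tables in section 10.3.1 have two attribution rows. One is labelled "Unrelated Unlikely"; the other covers possible, probable and definite. *Unlikely* is not among the four categories of section 10.3. Footnote 1 to each table limits its late-reporting rule to "Adverse events with attribution of possible, probable, or definite that occur greater than 30 days after the last dose".

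Section 10.3.2, on Unanticipated Problems, uses the same term with another meaning: there, possibly related is a reasonable possibility that the research procedures caused the event, and an alternative cause is no bar. Appendix D, section 8, repeats that meaning for network sites. The form in section 10.3.2.1 is triggered by serious events "deemed related or possibly related to the research drug, biologic or intervention".

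**The concern.** The scale is out of order. *Probably* allows a competing explanation, while the weaker *Possibly* forbids one. *Possibly* is also the only related category open to an event that follows no known pattern. A new type of event with any potential alternative cause is thus shut out of all three related categories.

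That combination should be common here. Every patient has advanced renal cancer and is planned to receive high-dose aldesleukin, for which section 6.2 lists a wide range of toxicities. The definitions judge causation by the investigational drug or agent; section 6.1.1 calls entinostat investigational, and section 6.2 calls aldesleukin commercially available. On that reading aldesleukin is itself an alternative cause. Yet the note closing section 6.1.4 warns that the combination may produce events seen with neither agent before, and monitoring toxicity is part of the Phase II primary objective (section 1.2.1). At stake is whether unexpected events of this kind reach the expedited-reporting system, and how fast.

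**Working it through.** No sample size or error rate is involved. The check sets the definitions and the two table rows side by side.

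**Step 1. Which category admits which event.** Three yes/no features (timely, known pattern, potential alternative cause) give 2 × 2 × 2 = 8 combinations. The four timely ones are:

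| Known pattern | Potential alternative cause | Category under section 10.3 |
|---|---|---|
| Yes | No | *Definitely* (or *Probably*) |
| Yes | Yes | *Probably* |
| No | No | *Possibly* |
| No | Yes | None of the three related categories; matches only the second sentence of *Unrelated* |

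The four combinations without timely onset match only the second sentence of *Unrelated* and are not at issue. In the last row above, the leading criterion of *Unrelated* is not met, because a merely potential alternative is not evidence that "there is evidence that it is definitely related to a cause other than the investigational drug/agent". The second sentence nevertheless describes the event, so that is where an investigator is likely to put it.

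**Step 2. What the misfiling changes within 30 days of the last dose.** The lower table row (possible, probable, definite) is compared with the upper one (unrelated, unlikely), column by column, in section 10.3.1. The columns that differ are:

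| Table | Unexpected event | If possible or higher | If unrelated or unlikely |
|---|---|---|---|
| Phase 1 | Grade 2 | 10 days | Not required |
| Phase 1 | Grade 3, no hospitalization | 24 hours/5 days | Not required |
| Phase 1 | Grade 3, hospitalization | 24 hours/5 days | 10 days |
| Phase 2 | Grade 2 | 10 days | Not required |
| Phase 2 | Grade 3, no hospitalization | 10 days | Not required |
| Phase 2 | Grade 4-5 | 24 hours/5 days | 10 days |

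That is 3 of 8 columns in Phase 1 and 3 of 9 in Phase 2. All six are for unexpected events; no column restricted to expected events changes. Four of the six lose a deadline altogether or move to not required from a 10-day or 24-hour rule; the other two move to a slower clock.

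**Step 3. More than 30 days after the last dose.** Footnote 1 covers unexpected grade 3 events with hospitalization, unexpected grade 4 events, and grade 5 events. The text under each table separately requires reports, whatever the attribution, for grade 3-5 events that cause or prolong hospitalization, for deaths on study, and for disability or birth-defect events. Removing those from the footnote's list leaves one clear loss: unexpected grade 4 events without hospitalization.

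**Step 4. Whether other rules depend on attribution.** The DLT definition (sections 4.1 and 11.2) and the sequential toxicity boundary (section 11.4) count extended grade 4 toxicity without reference to relatedness. Neither is affected.

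**The case against.** The strongest reply is that the protocol has many safeguards that ignore attribution. Besides those in step 3, every grade 4-5 event within 30 days is expedited on some clock. All serious events go to the Principal Investigator or Study Coordinator regardless of cause (section 10.3.1), and network sites report all of them to their IRB (Appendix D, section 7). Grade 3/4 toxicities are reviewed monthly (section 10.4), and events that are not expedited enter routine submissions. This stands, and it bounds the harm. It does not restore the expedited reports lost for unexpected grade 2 and non-hospitalized grade 3 events. Entinostat continues between aldesleukin cycles, when events of that kind can plausibly arise.

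A reader might infer more than the documents support, on four counts:

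- *That any new type of event has no category.* One without an alternative cause fits *Possibly*, and the second sentence of *Unrelated* does describe the excluded combination. Misfiling is the likelier failure.
- *That the Unanticipated Problem form fails for the same reason.* Section 10.3.2 has its own, broader definition. The fault is two meanings of one term.
- *That the entinostat rule in section 5.1 is distorted by aldesleukin as a competing cause.* That rule applies to the period off aldesleukin and does not cite the section 10.3 categories.
- *That late grade 3-4 events in general go unreported.* Step 3 shows a narrower loss.

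Two uncertainties remain. Section 10.3 speaks of study medication before it turns to the investigational drug or agent, so aldesleukin may or may not count as an alternative cause; the cancer itself remains one either way. *Unlikely* may be defined in the CTEP guidelines that section 10.3 cites, but these are not part of the documents, and such a definition would not mend the wording of *Possibly*.

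**Conclusion.** The point holds in this bounded form. Followed as written, section 10.3 prevents a timely event of no known pattern with a potential alternative cause from being called possibly related, in conflict with section 10.3.2 and Appendix D. If such an event is filed as *Unrelated*, three columns of each table change, all for unexpected events. Complete loss of the expedited report is confined to grade 2 and non-hospitalized grade 3 events within 30 days and, clearly, to non-hospitalized grade 4 events after that. The Phase 1 changes matter less from here on, since section 4.1 states that the recommended dose has been determined.

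The conclusion assumes that investigators apply the definitions literally and follow the second sentence of *Unrelated* when its two sentences disagree. The documents give no rate for such events, so the number of reports affected cannot be estimated. This is a faulty stated rule, not just missing detail, and it should be corrected.

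**What to change.** Amend the Relationship list in section 10.3:

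1. Reword *Possibly* to agree with section 10.3.2: timely onset and a reasonable possibility of causation, where an alternative cause may exist.
2. Limit *Unrelated* to events with evidence of a definite other cause, and remove or reword the second sentence so that a merely potential alternative is not enough.
3. Define *Unlikely*, so that section 10.3 has the same five categories as the tables in section 10.3.1.
4. State whether aldesleukin counts as study medication or as an alternative cause.

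The cost is an amendment to one list and the matching case report form field, plus a few more expedited reports, a number the documents do not allow to be estimated. The correction does not need timing alone to suffice for *Possibly*, nor separate attribution for each agent and for the combination; those are matters of preference.
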